3.4.3 Study period

The study period is the duration of the cluster or outbreak as defined by the study team.

☑ This should be detailed in study annexes.

Under certain circumstances the study period could be restricted to part of the duration of the cluster/outbreak if the influenza vaccination status changes substantially during this time period.

3.4.4 Exposure

Definition

For vaccinations requiring one dose (seasonal or pandemic vaccination)

An individual is considered vaccinated 14 days after vaccination is performed.

For children, for seasonal flu vaccination

- A child is considered fully vaccinated:
 - 14 days after he/she had the second of two influenza shots; or
 - 14 days after receipt of one influenza shot and was vaccinated in the previous influenza season.
- A child is considered partially vaccinated 14 days after receipt of one influenza shot in absence of vaccination the season before.

For pandemic vaccination requiring two doses:

If two doses of pandemic vaccine are required, the terms 'fully' and 'partially' vaccinated must be defined and applied.

Ascertainment

An individual should be considered as vaccinated against influenza if:

- he or she is registered as vaccinated in a vaccination registry;
- he or she reports having received influenza vaccination during the current season; or
- his or her insurance company can show evidence of pharmacy delivery or re-imbursement of influenza vaccination in the current influenza season.
- ☐ The precise mode of vaccine ascertainment in each study should be specified in study annexes.

The exposures of interest in this study are vaccination with pandemic influenza vaccine and trivalent seasonal influenza vaccine. The history of vaccination will include date of administration, type of vaccine (seasonal or pandemic), number of doses and brand name.

The investigation team must identify brands used in the area and compile a list of possible brands used.

3.4.5 Outcome

The primary outcome of interest is laboratory-confirmed influenza A(H1N1)v infection.

Secondary outcomes of interest are:

- persons meeting the EU influenza-like illness (ILI) case definition;
- persons meeting the H1N1 clinical criteria (case definition EU);
- hospitalisations, pneumonia, deaths (or other, if relevant to the cluster).

3.4.6 Cases

Case identification

Information on signs and symptoms of respiratory illness will be collected from all study participants and include:

- cough;
- sore throat;
- shortness of breath;
- fever:
- myalgia;
- headache:
- malaise.

All persons presenting with any of those signs and symptoms since the beginning of the cluster should be swabbed.

Mode of specimen collection, storage and transport for each study must be listed in the study annexes.

EU ILI definition

A case of ILI is defined as an individual presenting:

- sudden onset of symptoms AND at least one of the following four systemic symptoms:
 - fever or feverishness,
 - malaise,
 - headache,
 - myalgia,
- AND at least one of the following three respiratory symptoms:
 - cough,
 - sore throat,
 - shortness of breath.

Clinical criteria – from EU novel influenza virus A(H1N1) case definition (30/4/2009)

Any person with one of the following three:

- fever > 38°C AND signs and symptoms of acute respiratory infection,
- pneumonia (severe respiratory illness),
- death from an unexplained acute respiratory illness.

Laboratory confirmation

Influenza laboratory confirmation should be done using RT-PCR and/or culture.

RT-PCR characteristics for each study should be listed in study annexes.

Isolates should undergo a molecular analysis for currently circulating influenza A viruses (subtypes H3 and H1) and influenza B. A systematic subset should undergo gene sequencing.

Selection of isolates for each study should be specified in study annexes.

If rapid diagnostic tests (RDTs) are to be used for laboratory confirmation, then their sensitivity and specificity needs to have been studied and documented in a similar situation (e.g. similar study population).

3.4.7 Risk groups

Pandemic vaccine

According to ECDC interim guidance², the risk groups to be considered for the pandemic vaccine are:

- people aged less than 65 years with chronic underlying conditions, namely:
 - chronic respiratory diseases;
 - chronic cardiovascular diseases;
 - chronic metabolic disorders (notably diabetes);
 - chronic renal and hepatic diseases;

http://www.ecdc.europa.eu/en/publications/Publications/Forms/ECDC_DispForm.aspx?ID=388

² European Centre for Disease Prevention and Control (ECDC). Interim guidance: Use of specific pandemic influenza vaccines during the H1N1 2009 pandemic. Stockholm: ECDC; 2009. Available from:

- persons with deficient immunity (congenital or acquired);
- chronic neurological or neuromuscular conditions;
- any other condition that impairs a person's immunity or prejudices their respiratory function;
- young children (especially under the age of two years);
- pregnant women.

Other target groups may include healthcare workers, essential service workers, caregivers of infants < 6 months old.

Seasonal vaccine

Individuals are considered to belong to a risk group if their patient record contains any of the ICD codes listed on Table 1 or if they report having one of the underlying conditions included in the same table..

3.4.8 Confounding factors and effect modifiers

To control for differences in vaccinated compared to non-vaccinated individuals, information on potential confounding factors is collected.

The minimum confounding factors to be considered include chronic diseases, indicators of the severity of chronic diseases, current vaccination with seasonal flu vaccination (if IVE of pandemic vaccine is calculated), current vaccination with pandemic flu vaccination (if IVE of seasonal vaccine is calculated), previous influenza vaccination, antiviral drug use, smoking and functional status (the latter if cluster is in elderly people).

Below is a list of confounding factors and effect modifiers. Not all information will be relevant or available, given the nature of the cluster.

The precise information collected in each study should be specified in annexes.

Chronic diseases

An individual will be classified as belonging to a high risk group if:

- medical records indicate presence of chronic disease (see Table 1);
- he/she reports having the following underlying conditions:
 - diabetes if treated for insulin-dependent or non-insulin-dependent diabetes;
 - cardiovascular disease if has had any of the following: myocardial infarction, angioplasty, coronary artery bypass surgery, stroke, transient ischaemic attacks, treated hypercholesterolaemia, treated hypertension;
 - chronic pulmonary disease;
 - immunodeficiency.

Table 1: ICD and ICHPPC-2 codes for chronic diseases

Chronic diseases	ICD Code	ICHPPC-2 code
Anaemia spleen	280–289 and 759.0	B82
Cirrhosis	571	D97
Diabetes and endocrine	250 and 251	T89 and T90
Heart disease	093, 112.81, 130.3, 391, 393–398, 402, 404, 410–429, 745, 746, 747.1, 747.49, 759.82, 785.2, and 785.3	K71, K74-77, K81-K84, K86-K87 and K99
Haematologic cancer	200–208	B72 andB74
Immunodeficiency and organ transplant	042, 079, 279, V08, and V42	B99
Lung disease	011, 460, 462, 465, 466, 480–511, 512.8, 513–517, 518.3, 518.8, 519.9, and 714.81	A70, R83, R79, R95, R96 and R99
Non-haematologic cancer	140–198 and 199.1	A79, D74-D78, F74, H75, K72, L71, N74, N76, R84, R85, S77, S79, T71, T73, U75-U77, U79, W72-W73, X75-X77, X81 and Y77-Y
Nutritional deficiencies	254, 255, 259.2, and 260–269	T05 and T99
Renal disease	274.1, 408, 580–591, 593.71–593.73, and 593.9	U99
Dementia, stroke	290-294, 331, 340, 341, 348, and 438	P70 and K90
Rheumatologic diseases	446, 710, 714.0–714.4, 714.8, 714.89, and 714.9	L88

☐ The precise codes used in each study should be specified in study annexes.

Severity

The severity of the underlying conditions will be measured by the number of hospital admissions due to the underlying conditions in the year prior to study inclusion.

Smoking history

Smoking history will be collected and coded as 'never smoked', 'former smoker' (stopped smoking at least one year before inclusion in the study) and 'current smoker'.

Former vaccination

Former vaccination includes:

 Vaccination against influenza in the previous two years (collecting information on vaccination for each of the seasons).

Functional status (where applicable)

Information on functional status will be collected in terms of needing assistance with bathing.

Antiviral administration

Use of antivirals will be documented: type, dose and date of administration.

Other confounding factors that should be considered if available or relevant include:

- Level of social interaction
 - Number of household members
 - Children: nursery vs. school-age children
- Indicators of socio-economic status
 - Education level
 - Profession
 - Others (e.g. deprivation score by area of residence)
- Any other available and relevant for the study population

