3.4.10 Data

Data collection

Data will be collected from all study participants using a standardised questionnaire. The procedures to collect data should be defined by each study coordinator (e.g. face-to-face, by telephone, postal questionnaire, web-based, etc.).

Double data entry is needed.

Details on data collection methods, data entry and data transmission should be specified in study annexes.

Information collected

(see Annex)

- Study participant demographics
- Signs, symptoms
- Severity: hospitalisation, pneumonia, death
- Date of onset of symptoms
- Date of swabbing
- Laboratory results
- Selected underlying chronic conditions (including diabetes, heart disease, chronic obstructing pulmonary disorder and immunodeficiencies);
- Number of hospitalisations in the previous year (if relevant)
- Number of GP visits in the previous year (if relevant)
- Smoking history
- Current influenza vaccination(s) including date of vaccination, type (seasonal, pandemic), doses and brand (if possible)
- Former influenza vaccination
- Functional status (if relevant)
- Pregnant: yes/no (if relevant)
- Use of antivirals, type, dose and date of administration
- Information on respiratory symptoms or laboratory-confirmed A(H1N1) influenza since the beginning of the pandemic in their country (or other date according to the duration of the pandemic) and prior to the cluster/outbreak

Data validation

If data are collected using paper questionnaires, a sample of paper questionnaires should be checked against the study database to validate data entry.

The specific validations procedures should be specified in study annexes.

Data cleaning

Summary and frequency tables and graphic displays of appropriate variables will be used to find illegal, implausible or missing values within the dataset. Checks for inconsistencies will be carried out (e.g. date of swabbing before date of onset of symptoms). These values will be checked against the questionnaires or queried

with the study participant. Any changes to the data will be documented and stored separately from the crude database. Any recoding of data (e.g. age from date of birth) will be documented.

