3.4.11 Analysis

Analyses will be carried out separately for seasonal and pandemic IVE and for different vaccine brands.

Separate analyses will be carried out for the different primary and secondary outcomes.

Analyses will be carried out including and excluding persons with recent respiratory symptoms (prior to cluster) that were not lab-confirmed, where information is available.

An analysis will be carried out including only persons 'fully vaccinated' in the vaccinated group. A second analysis will include persons 'fully' and 'partially vaccinated' in the vaccinated group.

Descriptive and univariable analyses

Participation variables include:

- total number not eligible
- total number eligible
- total number included: vaccinated and unvaccinated; and
- total number of subjects that refused participation.

Study population baseline characteristics by influenza vaccination status

Baseline characteristics include:

- Age
- Gender
- Socio-economic status indicators
- Comorbidities
- Functional status (if relevant to cluster)
- Pregnancy status
- Previous vaccination (influenza)
- Antiviral use
- Smoking history

Baseline characteristics of vaccinated and unvaccinated participants will be described using proportions and mean/medians (depending on variable type). Missing data for each characteristic will be described, along with approaches on how the missing data were dealt with.

In order to test for differences between vaccinated and unvaccinated characteristics, Student's t test, Mann-Whitney test, chi-square test or Fisher's exact test will be used (depending on the nature and the sample size).

Table 4: Study population baseline characteristics by influenza vaccination status:

(to be completed/modified according to the variables collected)

Characteristics	Vaccinated (N =)	Unvaccinated (N =)
Demographic		
Age		
• Sex		
 Socio-economic status 		
Comorbidities		
Functional status (if relevant)		
Pregnancy status		
Previous flu vaccination		
Antiviral use		
Smoking history		

Crude VE estimates

The vaccine effectiveness will be computed as $VE = (1 - RR) \times 100$; exact 95% CI are computed around the estimate for each outcome.

Stratified analysis

Analysis should be stratified according to:

- age groups;
- presence or absence of high risk conditions;
- effect modifiers are assessed one by one comparing the RR across the strata of the baseline characteristic;

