- confounding is assessed by comparing crude and adjusted RR for each baseline characteristic.

Multivariable analysis

A multivariable analysis is conducted to control for negative and positive confounding. Variables will be tested for multicollinearity.

The type of multivariable analysis depends on the nature (high or low incidence) of the cluster and the type of denominator used (persons or person-time). Regression methods could include Cox, Poisson or logistic regression.

The multivariable analysis type and model building strategy should be specified in study annexes.

Sensitivity analysis

In order to assess effects of a potential confounding factor not included in the analysis on VE estimates, a sensitivity analysis could be conducted.

Any sensitivity analysis carried out should be specified in study annexes.

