vacc_05	Numeric (categorical)	0 = No 1 = Yes 8 = Don't know	Previous influenza vaccination 2005–6
vacc_04	Numeric (categorical)	0 = No 1 = Yes 8 = Don't know	Previous influenza vaccination 2004–5
Diabetes	Numeric (categorical)	0 = No 1 = Yes 8 = Don't know	Diabetes and endocrine
heart_dis	Numeric (categorical)	0 = No 1 = Yes 8 = Don't know	Heart disease
immune	Numeric (categorical)	0 = No 1 = Yes 8 = Don't know	Immunodeficiency and organ transplant
Lungdis	Numeric (categorical)	0 = No 1 = Yes 8 = Don't know	Lung disease
Severity	Numeric (count)	integer	Number of hospitalisations in the previous year for the chronic disease
fs_bath	Numeric (categorical)	0 = No 1 = Yes 8 = Don't know	Requires assistance to bath
Pregnant	Numeric (categorical)	0 = No 1 = Yes 8 = Don't know	Pregnancy status
Smoking		0 = Never 1 = Former 2 = Current 9 = Don't know	Never, former (stopped smoking at least one year before inclusion in the study), current smoker
Antivir	Numeric (categorical)	0 = No 1 = Yes 8 = Don't know	Recent use of antivirals
Antivirdate	Date	dd/mm/yyyy	Date of antiviral administration
Antivirdose	Text		Doses of antiviral taken
Antivirbrand	Text		Type of antiviral taken (brand name)
ili_prior	Numeric (categorical)	0 = No 1 = Yes 8 = Don't know	ILI since beginning of pandemic, but prior to cluster
Ili_prior_lab	Numeric (categorical)	0 = Negative 1 = Positive 2 = Not done 8 = Don't know	Laboratory result (positive/negative)
ili_prior_virus	Text		Laboratory result: virus type and subtype of recent ILI
contra	Numeric (categorical)	0 = No 1 = Yes 8 = Don't know	Exclusion criteria: contraindication for influenza vaccination

This table represents a selection of covariates. Variables can be included or excluded as necessary.

Other annexes containing details of specific studies should be added to the current protocol.

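### Antiviral use is listed as a baseline confounder without limiting it to use before symptom onset, so in the cohort design treatment of cases can be flagged as confounding and pull RR-based VE toward the null

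*Protocol*

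**What the plan says.** **Confounder list.** Protocol section 3.4.8 opens its list with "The minimum confounding factors to be considered include chronic diseases, indicators of the severity of chronic diseases" and continues to "previous influenza vaccination, antiviral drug use, smoking and functional status (the latter if cluster is in elderly people". The case-control section on confounding factors and effect modifiers carries the same list. Section 3.4.8 qualifies it: "Not all information will be relevant or available, given the nature of the cluster".

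**Data.** Section 3.4.8 adds: "Use of antivirals will be documented: type, dose and date of administration". No rule relates that date to symptom onset, although section 3.4.10 also collects "Date of onset of symptoms". The Annex has a yes/no/don't know variable defined as "Recent use of antivirals", plus fields for date, doses and brand.

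**Cohort analysis.** Section 3.4.11 includes "Antiviral use" among the baseline characteristics and again in Table 4. Under stratified analysis it states that "confounding is assessed by comparing crude and adjusted RR for each baseline characteristic". The type of multivariable model and the model-building strategy are left to study annexes.

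**Case-control analysis.** The preferred logistic model in section 3.5.11 contains current and former vaccination, chronic conditions, age, sex, smoking and functional status. Antiviral use is not in it.

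**The concern.** In an influenza cluster, antivirals may be taken for two reasons: as prophylaxis before illness, or as treatment once ill. Prophylaxis can confound, because it may be related to vaccination and may change the risk of infection. Treatment of a case is a consequence of the outcome. It is neither a baseline characteristic nor a confounder, and conditioning on it distorts the risk ratio.

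The protocol merges the two. Other covariates in section 3.4.8 are anchored in time: severity uses admissions in the year before inclusion, and former smoking is defined relative to inclusion. Antiviral use has no such anchor, and the word recent in the Annex is tied neither to onset nor to the start of the cluster.

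At stake is the adjusted VE for the primary objective in cohort investigations. This is a core template for national and local teams, so a misclassified variable in its lists and Table 4 can carry into many annexes.

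**Working it through.** The protocol gives no figure on this point, so there is none to reproduce. The check asks what the crude-versus-adjusted comparison does when antivirals are given after the outcome and there is no confounding at all.

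**Inputs**
- From Table 3: attack rate 20% in the unvaccinated, RR 0.5, ratio of unvaccinated to vaccinated 1 (coverage 50%).
- Assumed, because the protocol gives no treatment shares: 60% of cases and 5% of non-cases take antivirals, regardless of vaccination.

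**Expected counts per 1,000 vaccinated and 1,000 unvaccinated**

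| | Vaccinated cases | Vaccinated non-cases | Unvaccinated cases | Unvaccinated non-cases |
|---|---|---|---|---|
| Antiviral | 60 | 45 | 120 | 40 |
| No antiviral | 40 | 855 | 80 | 760 |
| Total | 100 | 900 | 200 | 800 |

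**Crude RR** = (100/1000)/(200/1000) = 0.50, so VE = 50%, the true value.

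**Stratum RRs.** With antivirals: (60/105)/(120/160) = 0.762. Without: (40/895)/(80/840) = 0.469.

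**Mantel-Haenszel RR** = Σ[a(c+d)/T] / Σ[c(a+b)/T], where a and b are vaccinated cases and non-cases, c and d unvaccinated cases and non-cases, and T the stratum total:
- numerator: 60×160/265 + 40×840/1735 = 36.23 + 19.37 = 55.59
- denominator: 120×105/265 + 80×895/1735 = 47.55 + 41.27 = 88.82
- RR = 0.626, VE = 37.4%. A Poisson model with vaccination and antiviral use gives 37.8%.

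The comparison therefore moves from 0.50 to about 0.63 and would mark antiviral use as a confounder, although by construction it is not one.

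**Range over the assumed shares** (attack rate 20%, true VE 50%, Poisson-adjusted)

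| Cases treated | Non-cases treated | Adjusted VE |
|---|---|---|
| 60% | 5% | 37.8% |
| 30% | 5% | 46.7% |
| 20% | 5% | 48.6% |
| 60% | 30% | 48.3% |
| 30% | 20% | 49.8% |

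With 60% v 5%, attack rates of 10/20/30/40% give 41.0/37.8/36.6/36.4%. At the more extreme 80% v 5%, the Mantel-Haenszel figures for the same attack rates are 34.1/28.7/26.3/25.4%.

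**Odds ratio.** In the count table, the crude OR is 100×800/(900×200) = 0.444. The stratum ORs are 60×40/(45×120) = 0.444 and 40×760/(855×80) = 0.444. Adjustment leaves 1 − OR at 55.6%. The OR moves only if treatment also differs by vaccination status. At the same attack rate, with 5% of non-cases treated, the Mantel-Haenszel 1 − OR becomes 46.7% if 40% of vaccinated and 60% of unvaccinated cases are treated, and 62.3% if the shares are reversed.

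**With a pre-onset variable.** If only use before onset counts and it is unrelated to vaccination and infection, both strata have RR 0.50 and adjusted VE stays at 50%.

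**The case against.** The strongest reply is that the protocol does not order this adjustment. The list is of factors to be considered, with an allowance for items that are not relevant or available. Table 4 may be modified, and the Annex lets variables be included or excluded. The cohort model belongs to the study annexes, and the preferred case-control model omits antivirals. Antiviral and onset dates are both collected, so a careful team can already separate prophylaxis from treatment.

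Most of this stands, and it rules out two stronger readings. A reader might infer that antiviral use is a mandatory adjustment variable. The text does not say so for either design. A reader might also infer that VE is biased in every analysis. The OR is unchanged when treatment depends only on case status, and no passage gives treatment shares by vaccination status. The Background does mention directing antivirals to subgroups in which the vaccine is less effective. That makes differential use plausible but does not quantify it.

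The size also depends wholly on assumed shares. With few cases treated, or wide use in non-cases, the shift is a point or two.

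The reply does not remove the cohort problem. The protocol itself calls the variable a baseline characteristic and prescribes a comparison that treatment of cases will trip. Leaving model building to annexes does not correct the label or the screening rule that annex authors start from.

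**Conclusion.** The point holds for RR-based cohort analyses. Followed as written, the cohort text can flag antivirals given because of illness as a confounder and open the way to adjusting for them. In every scenario calculated this moved VE toward the null. With a true VE of 50% and a 20% attack rate, adjusted VE runs from about 38% (60% of cases v 5% of non-cases treated) to almost 50% (30% v 20%). These figures rest on assumed treatment shares, 50% coverage, no true confounding, and treatment unrelated to vaccination.

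For OR-based analyses the point is conditional on treatment also differing by vaccination status. In the case-control design it concerns the confounder list rather than the preferred model. This is an incorrect classification in the protocol, not merely detail left to a later analysis plan.

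**What to change.** 1. In section 3.4.8, the case-control section on confounding factors and the Annex, define the covariate as antiviral use started before symptom onset for cases, and before a comparable reference date for non-cases or controls.
2. Fix the reference date so that cases and non-cases have comparable windows. Counting use up to onset in cases but up to the end of the outbreak in non-cases would create a new bias. Options are use before the start of the cluster for everyone, or risk-set matched or time-dependent use where person-time is analysed. The first is simplest but misses prophylaxis begun during the cluster.
3. State that use on or after onset is not adjusted for.
4. Replace the unrestricted item in the cohort baseline list and Table 4 with the pre-onset variable. Later use can still be described separately.

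The cost is a revised definition and a little more data derivation from the antiviral and onset dates already collected. The result depends on complete antiviral dates. The Annex has a single antiviral date field, so it should say that this is the first administration. This is an analysis definition only and changes nothing about who receives antivirals.

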A multivariable (conditional, if matched) logistic regression analysis will be conducted to control for negative and positive confounding. Odds ratios and standard errors will be obtained. Preferably, the model will include: current influenza vaccination, former influenza vaccination, underlying chronic conditions, age, sex and smoking and functional status. Variables will be tested for multicollinearity. Interactions will be tested for using the Likelihood Ratio test (or Wald test) and included in the model if significant at 5% level. Factors other than statistical significance will also be used as criteria for inclusion of an interaction term.

4 Limitations

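### The chronic-disease code list takes in acute respiratory infection, pneumonia and influenza with no date limit, so where coded records are used an outbreak episode or an old infection can make a person high risk

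*Protocol*

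**What the plan says.** Protocol section 3.4.8 defines high-risk status partly from records: "medical records indicate presence of chronic disease (see Table 1"). Table 1 is a list of chronic diseases, and its lung disease row reads "011, 460, 462, 465, 466, 480–511, 512.8, 513–517, 518.3, 518.8, 519.9, and 714.81". Table 5 in the case-control part carries the same row. For the seasonal vaccine, section 3.4.7 is more literal: "Individuals are considered to belong to a risk group if their patient record contains any of the ICD codes listed on Table 1". Section 3.5.7 says the same with reference to Table 5.

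The resulting variable is used in three ways:
- Both designs stratify by "presence or absence of high risk conditions" (sections 3.4.11 and 3.5.11).
- Chronic disease heads the minimum set of confounders to be considered in sections 3.4.8 and 3.5.8.
- The preferred case-control model contains "current influenza vaccination, former influenza vaccination, underlying chronic conditions, age, sex and smoking and functional status".

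The secondary outcomes in section 3.4.5 include "hospitalisations, pneumonia, deaths (or other, if relevant to the cluster"), and pneumonia alone also meets the H1N1 clinical criteria in section 3.4.6.

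**The concern.** The tables do not name the ICD revision, but the format does: 250 for diabetes, 571 for cirrhosis, 410–429 for heart disease, and V codes in the immunodeficiency row ("042, 079, 279, V08, and V42"). That is ICD-9. In that classification 460, 462, 465 and 466 are acute nasopharyngitis, pharyngitis, upper respiratory infection and bronchitis. The unbroken range 480–511 includes pneumonia (480–486) and influenza (487–488).

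Neither risk rule says when the code must have been recorded. The neighbouring severity variable does have an anchor: admissions in the year before inclusion. Two errors follow where coded records are searched:

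1. **Outbreak codes.** A participant without chronic disease whose influenza or pneumonia in this cluster is coded becomes high risk because of the outcome.
2. **Old acute codes.** One past infection puts a person without chronic disease into the risk group, so the variable no longer separates those with chronic illness from those without.

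Section 4.2 relies on chronic-disease adjustment and risk-group stratification to limit negative confounding, so both errors bear on VE itself.

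**Working it through.** The protocol states no figure for this, so there is nothing to reproduce. The illustrations use a true RR of 0.5 in everyone, and attack rates of 10–40% in the unvaccinated, both from the planning tables in section 3.4.9. Everything else is assumed:
- f is the share of cases without chronic disease who acquire a listed code during the outbreak.
- g is the share of people without chronic disease who already carry an old acute code, unrelated to vaccination or outcome.
- There are 1000 people per arm.

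Adjusted estimates are Mantel-Haenszel, with a and c the cases among n1 vaccinated and n0 unvaccinated in a stratum of size N:

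RR = Σ(a·n0/N) / Σ(c·n1/N); OR = Σ(a·(n0−c)/N) / Σ(c·(n1−a)/N).

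**A. Equal chronic prevalence (20% in each arm), outbreak codes only**

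Attack rate 30%, f = 0.5. Vaccinated: 30 cases in 200 chronic and 120 in 800 others, of which 60 move. Unvaccinated: 60 in 200 and 240 in 800, of which 120 move.

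- Labelled high risk: 90/260 against 180/320. RR = 0.346/0.5625 = 0.615, VE 38.5%.
- Labelled not high risk: 60/740 against 120/680. RR = 0.0811/0.1765 = 0.459, VE 54.1%.
- Adjusted RR = (90·320/580 + 60·680/1420) / (180·260/580 + 120·740/1420) = 78.39/143.2 = 0.547, VE 45.3%.
- Stratum ORs: (90/170)/(180/140) = 0.412 and (60/680)/(120/560) = 0.412. The true OR is (0.15/0.85)/(0.30/0.70) = 0.412, so they are unchanged.

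The same steps for other values:

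| Attack rate | f | VE (RR), high risk | VE (RR), not high risk | Adjusted VE (RR) |
|---|---|---|---|---|
| 10% | 0.1 | 49.0% | 50.3% | 49.9% |
| 10% | 0.3 | 47.2% | 50.8% | 49.2% |
| 30% | 0.1 | 47.2% | 50.8% | 49.8% |
| 30% | 0.3 | 42.4% | 52.4% | 48.2% |
| 30% | 0.5 | 38.5% | 54.1% | 45.3% |
| 40% | 0.5 | 35.7% | 55.6% | 44.6% |

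**B. Chronic disease commoner in the vaccinated, the situation section 4.2 describes**

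Assumed: 40% of vaccinated and 10% of unvaccinated are chronic; risk in the unvaccinated is 30% if chronic and 15% otherwise. Vaccinated: 60 cases in 400 chronic and 45 in 600 others. Unvaccinated: 30 in 100 and 135 in 900. Crude RR = 105/165 = 0.636 (VE 36.4%).

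| Classification | High risk (vacc. / unvacc.) | Not high risk (vacc. / unvacc.) | Adjusted RR | VE (RR) | Adjusted OR | VE (OR) |
|---|---|---|---|---|---|---|
| Correct | 60/400; 30/100 | 45/600; 135/900 | 39.00/78.00 | 50.0% | 31.35/70.35 | 55.4% |
| Outbreak codes, f = 0.3 | 73.5/413.5; 70.5/140.5 | 31.5/586.5; 94.5/859.5 | 37.36/90.95 | 58.9% | 25.95/79.54 | 67.4% |
| Outbreak codes, f = 0.5 | 82.5/422.5; 97.5/167.5 | 22.5/577.5; 67.5/832.5 | 36.71/97.47 | 62.3% | 22.00/82.76 | 73.4% |
| Old codes only, g = 0.3 | 73.5/580; 70.5/370 | 31.5/420; 94.5/630 | 47.53/80.84 | 41.2% | 39.24/72.55 | 45.9% |
| Old codes only, g = 0.5 | 82.5/700; 97.5/550 | 22.5/300; 67.5/450 | 49.80/81.60 | 39.0% | 41.34/73.14 | 43.5% |

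Outbreak codes overcorrect. Old codes pull the adjusted estimate back towards the crude one. The errors act in opposite directions here, so their net effect in a given cluster cannot be predicted from the documents.

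**C. Pneumonia outcome.** If a share k of pneumonia outcomes in people without chronic disease is coded in the searched record, only 1 − k of them stay in the not-high-risk stratum.

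**The case against.** **The meanings of the codes are not printed.** True. The reading rests on the standard ICD-9 classification, identified from the format and the other rows. The table's chronic-disease label shows the intent, but the seasonal rule still applies "if their patient record contains any of the ICD codes listed on Table 1", so the list decides.

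**This is a template.** Sections 3.4.8 and 3.5.8 ask each study to specify its codes in an annex, and the variable list may be adapted. That allows a repair. It does not flag the acute codes or ask for a date limit, so the printed default stands unless someone notices.

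**Much of the setting escapes.** Data come by questionnaire, and the self-report route names chronic pulmonary disease. Where status is self-reported only, the mechanism does not arise. The pandemic-vaccine risk groups in sections 3.4.7 and 3.5.7 are described without codes, so the any-code wording belongs to the seasonal rule. The high-risk confounder definition in 3.4.8 and 3.5.8 nevertheless points to the same tables.

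**Stronger readings that the documents do not support**
- *Both designs are always biased.* In illustration A the stratum ORs do not move, so a traditional case-control study or a logistic cohort analysis shows no distortion there. OR bias needs chronic disease to differ by vaccination status, as in B. A case-cohort OR approximates the RR, so the RR results are the relevant ones for that design.
- *Risk status is a mandatory confounder.* The protocol lists factors to be considered, accepts that some will be unavailable, and states the model as a preference.
- *VE against pneumonia cannot be estimated in the not-high-risk stratum.* Pneumonia is its own variable in the Annex, not a code search. The stratum is emptied of it only if every such outcome is coded in the searched record (k = 1).

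**Conclusion.** The point holds as a defect in the printed definition. Tables 1 and 5 count acute respiratory infection, pneumonia and influenza as chronic lung disease, and the risk rules have no cut-off date. Where coded records are used, high-risk status can follow from the outcome or from an irrelevant past infection.

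The size depends on f and g, which the documents do not give. At f = 0.1 with equal prevalence, adjusted VE is practically unchanged. At f = 0.5 and attack rates of 30–40% it falls to about 45% by RR, with apparent effect modification that is not real. With the unequal prevalence assumed in B, adjusted VE moves from 50% to 59–62% or 39–41% by RR, and from 55.4% to 67.4–73.4% or 43.5–45.9% by OR. VE against pneumonia in the not-high-risk stratum is distorted to the extent that pneumonia is coded in the searched record. The stratified estimates are secondary objectives, subject to sample size. This should be corrected, but it does not undermine the design.

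**What to change.** - In Tables 1 and 5, remove 460, 462, 465 and 466 and the pneumonia and influenza part of 480–511 (480–488), keeping the rest of the range.
- Check the ICHPPC-2 column of the same row for acute conditions; it has not been examined here.
- In sections 3.4.7, 3.4.8, 3.5.7 and 3.5.8 (confounding factors), state that only conditions recorded before the beginning of the outbreak count.

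The edit to the list and the date rule are both needed. A date limit alone leaves old acute codes in. Trimming the list alone still lets any other listed condition first recorded during the outbreak change a person's risk status. In illustrations A and B, f = 0 and g = 0 restore the true values.

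The cost is an edit to two identical rows and one sentence in each section, plus the date of each recorded condition where records are searched. Fewer people will be classed as high risk, so the aim in section 3.5.11 of 80 cases and 80 controls per stratum becomes harder to reach.
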